11.6.1 Dose reduction steps for bosutinib

In case of a toxicity event possibly related to bosutinib, a dose reduction from 400 mg to 300 mg, unless the toxicity resolves (Grade ≤ 1) is permitted. If a patient requires a second dose reduction from 300 mg to 200 mg, the Investigator should contact the Sponsor to determine if the patient may continue on treatment at a lower dose. The second dose reduction must be approved by the sponsor and will only be considered if the patient in question displays optimum response to bosutinib treatment at the time-point at which the dose reduction is being considered. Patients should remain on the 200 mg dose for a maximum of 4 weeks or until the toxicity resolves, whichever is sooner. In line with the dose reduction and dose escalation guidelines detailed, the dose can then be re-escalated following the escalation guidelines. Any patient on the 200 mg dose with ongoing toxicity after the 4-week point will be discontinued from treatment and will continue with Follow-up evaluations. Dose reductions of bosutinib below 200 mg will not be permitted.

If the Investigator and the Sponsor decide that it is not in the best interest of the patient to remain on treatment at a dose lower than 300 mg/day, the patient will be discontinued from treatment and will continue with Follow-up evaluations.

Once the dose has been reduced for a patient, the patient should remain on that dose unless the toxicity resolves (Grade ≤ 1). In that case, the dose can be escalated to the previous starting dose.

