11.6.1.1 Management of Non-Hematologic Treatment-Related Toxicities

The management of non-hematologic treatment-related toxicities is summarized in Table 1.

Table 1. Non-Hematologic Treatment-Related Toxicities

Adverse Event	Action
Elevated liver transaminases	If elevations in liver transaminases (ALT, AST) $> 5 \times$ institutional upper limit of normal (ULN) occur, bosutinib should be interrupted until recovery to $\leq 2.5 \times$ ULN and may be resumed at 400 mg once daily thereafter. If recovery takes longer than 4 weeks, discontinuation of bosutinib should be considered. If transaminase elevations $\geq 3 \times$ ULN occur concurrently with bilirubin elevations $> 2 \times$ ULN and alkaline phosphatase $< 2 \times$ ULN, bosutinib should be discontinued.
Diarrhea	For Grade 3/4 diarrhea, bosutinib should be interrupted and may be resumed at 400 mg once daily upon recovery to Grade ≤ 1 .
Grade 1	Current dose level

Grade 2	For persistent clinically relevant toxicity ^b not responding to optimal management: Temporarily interrupt treatment, and reintroduce at the same dose or reduce dose by 1 level upon recovery to Grade ≤ 1 within 4 weeks of stopping test article.
Grade 3 ^a	For persistent clinically relevant toxicity ^b not responding to optimal management: Withhold treatment, then dose reduce by 1 level upon recovery to Grade ≤ 1 within 4 weeks of stopping test article. If recovery takes longer than 4 weeks, the Investigator should contact the Sponsor to determine if the patient may continue on treatment.
Grade 4 ^a	Withhold treatment. Investigator and Sponsor to review to determine if patient may continue on treatment with appropriate dose reduction.
	
a. For patients requiring dose reduction due to toxicity, who have been free of the toxicity (Grade ≤ 1) for at least 1 month and are otherwise tolerating study drug, the Investigator may choose to re-escalate dose by 1 dose level back to starting dose.b. Persistent Clinically Relevant Toxicity is defined as - symptoms of toxicity which, despite optimal medical management, persist for ≥ 14 days ("persistent") and cause sufficient symptoms or signs of illness in the subject to warrant further intervention, i.e. dose adjustment ("clinically relevant").

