Subjects with Grade 3 non-hematological toxicity that does not respond to optimal management, will be managed by withholding treatment, followed by dose reduction by 1 level upon recovery to Grade ≤ 1 . If, on re-challenge at reduced dose, the subject remains free of toxicity (Grade ≤ 1) for at least 1 month, the Investigator may choose to re-escalate the dose by 1 level back to the starting dose.

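### After Grade 3-4 toxicity the protocol gives two bosutinib re-escalation rules, one with no wait and one with at least a month, and the 200 mg time limit does not fit the second

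*Protocol*

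**What the plan says.** **Protocol 11.6.1, closing paragraph.** A reduced patient stays on the lower dose unless toxicity resolves to Grade ≤1. Then: "In that case, the dose can be escalated to the previous starting dose". The sentence gives no wait and no limit to one level, and it is not restricted by toxicity grade.

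**Protocol 11.6.1, 200 mg step.** The second reduction (300 to 200 mg) needs Sponsor approval. "Patients should remain on the 200 mg dose for a maximum of 4 weeks or until the toxicity resolves, whichever is sooner". After that, "In line with the dose reduction and dose escalation guidelines detailed, the dose can then be re-escalated following the escalation guidelines". Toxicity still present after 4 weeks at 200 mg leads to discontinuation.

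**Protocol 11.6.1.1, Table 1 (non-hematologic).**
- Grade 3: "Withhold treatment, then dose reduce by 1 level upon recovery to Grade" ≤1.
- Note a, attached to Grades 3 and 4, applies to patients free of the toxicity (Grade ≤1) for "at least 1 month and are otherwise tolerating study drug, the Investigator may choose to re-escalate dose by 1 dose level", and names the starting dose as the target.
- Grade 2: "Temporarily interrupt treatment, and reintroduce at the same dose or reduce dose by 1 level upon recovery to Grade" ≤1. Note a is not attached to this row.
- Diarrhea, Grade 3/4: "bosutinib should be interrupted and may be resumed at 400 mg once daily upon recovery to Grade" ≤1. The transaminase row has a similar restart at 400 mg.

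**Protocol 11.6.1.1, text after Table 1 (Grade 3 non-hematologic).** A patient who stays at Grade ≤1 on re-challenge at the reduced dose qualifies "for at least 1 month, the Investigator may choose to re-escalate the dose by 1 level back to the starting dose".

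**Protocol 11.6.1.2, Table 2 (hematologic).** Grade 3 toxicity that needs more than 2 but no more than 4 weeks of hold leads to a one-level reduction. Recurrent Grade 3 toxicity leads to a reduction on recovery to Grade ≤2. Note a repeats the one-month, one-level condition for Grades 3 and 4.

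The SAP contains no dose-modification rules.

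**The concern.** One decision, when a patient reduced for Grade 3-4 toxicity may go back up, has two answers in the same section. A site that waits a month complies with both. A site that does not wait can cite the closing sentence of 11.6.1, yet departs from the condition in note a.

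The stake is patient safety: early or uneven re-exposure, across up to 10 centers, to the dose that preceded a severe toxicity, in a trial whose primary objective is the safety of bosutinib 400 mg/day in combination. It also affects conduct. Section 11.6 sends exceptions to the Medical Monitor, and section 17.9 has significant deviations reported. Neither works cleanly if the text does not settle what counts as compliant.

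**Working it through.** The plan states no figure to reproduce. The check sets the rules side by side and counts days.

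**Inputs**
- Dose levels: 400, 300 and 200 mg (Protocol 11.6.1).
- One month = one cycle = 28 days (Protocol 12.1, stated for visit scheduling). A calendar month would be up to 31 days.
- k = days from the start of 300 mg until Grade ≤1.
- d = day at 200 mg on which toxicity resolves, 0 to 28.

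**From 300 mg to 400 mg**
- 11.6.1 closing sentence: 400 mg possible on day k.
- Note a: 400 mg possible on day k + 28 (k + 31 with a calendar month).
- Difference: (k + 28) − k = 28 days (up to 31).

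*Table 1, Grade 3.* The reduced dose starts only once Grade ≤1 is reached, so k = 0. The rules give day 0 and day 28. Taken literally, the closing sentence lets the required reduction be reversed on the day it starts.

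*Table 2, Grade 3.* The reduced dose can start at Grade 2. Assume Grade ≤1 comes 7 days later (k = 7): day 7 against day 7 + 28 = 35 (38 with a calendar month). Over an assumed range of k from 0 to 28: days 0-28 against days 28-56.

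**From 200 mg to 400 mg**
- 11.6.1 closing sentence: 400 mg possible on day d.
- Note a, read as a return to the starting dose after one wait: day d + 28, a gap of 28 days.
- Note a, read as one level per wait: 300 mg on day d + 28, 400 mg on day d + 56, a gap of 56 days.

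From 300 mg, one level up is the starting dose, so the wording is consistent. From 200 mg, one level up is 300 mg and the starting dose is 400 mg, so the wording cannot mean both. The documents support a gap of 28 to 56 days (up to 62 with calendar months).

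**Does the 200 mg limit fit a toxicity-free month?**
- The stay ends on day d, which leaves d − d = 0 days at 200 mg after resolution, against 28 required.
- If only the 4-week cap applied, 28 − d days would remain. That reaches 28 only when d = 0.
- A toxicity-free month at 200 mg would end on day d + 28, beyond the 4-week cap for every d above 0.

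Note a does not say whether time on hold counts toward the month. Counting it might make the limit workable for some patients. For Grade 3 non-hematologic toxicity, however, the text after Table 1 counts the month on the reduced dose.

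**Where there is no conflict.** For Grade 2 non-hematologic reductions, 11.6.1 is the only rule. The transaminase and diarrhea rows have their own restart rules.

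**The case against.** The best defence is that 11.6.1 is general text and its two subsections supply the detail. The 200 mg paragraph does refer to escalation guidelines, and the only ones given are in those subsections. Reversing a Table 1 reduction on its first day would make that row pointless, so a sensible investigator would follow note a. Note a is also permissive and does not forbid an earlier return. This softens the conflict but does not remove it. The closing sentence has no pointer to the tables, and importing the one-month wait is what makes the 200 mg limit unworkable.

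The controls also count. Exceptions need Medical Monitor approval (11.6), Grade 4 toxicity needs Investigator and Sponsor review before treatment continues (Tables 1 and 2), and 200 mg needs Sponsor approval. A reader might infer that any site may return any Grade 3-4 patient to 400 mg at once and unsupervised. The documents do not support that for Grade 4 or for 200 mg. The Medical Monitor control is weaker for Grade 3, because an immediate return is an exception only if note a governs.

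A reader might also infer that prompt return to 400 mg is unsafe in itself. The protocol does not take that position: it allows such a return after Grade 3/4 diarrhea and after transaminase elevations. The defect is that two rules cover the same toxicities.

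**Conclusion.** The protocol is wrong as written on this point, in a limited way. For Grade 3-4 reductions outside the transaminase and diarrhea rows, the minimum wait at Grade ≤1 before going from 300 to 400 mg is 0 days under one rule and at least 28 under the other. From 200 to 400 mg the gap is 28 to 56 days. Both figures take a month as 28 days. The day counts in the hematologic example rest on the assumed k; the 28-day difference does not. The 200 mg exit rule and a toxicity-free month at that dose do not fit together.

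The documents give no frequency of dose reductions, so the number of patients affected is unknown. No sample size or interval changes.

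Two stronger readings are not supported:
- *That the group 1 DLT decision is materially at risk.* During the combination, related Grade 3 or 4 clinically evident non-hematologic toxicity is already a DLT, as is related Grade ≥3 toxicity needing more than 14 days to reach Grade ≤1 (Protocol 9.3.1). Later re-escalation cannot remove such a patient from the count.
- *That doses above 400 mg are authorised.* Section 11.6.1.2 mentions escalation for suboptimal response, but neither document gives criteria or a dose for it.

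**What to change.** 1. Replace the last sentence of 11.6.1 with: *After a reduction for Grade 3-4 toxicity, the dose may be re-escalated by one level (200 to 300 mg, 300 to 400 mg) only after at least 1 month (28 days) at Grade ≤1 on the reduced dose, as in note a of Tables 1 and 2; the transaminase and diarrhea rows of Table 1 keep their own restart rules.*
2. In note a of both tables and in the text after Table 1, change the wording on return to the starting dose to: *by one level, up to the starting dose*.
3. Keep the 4-week cap at 200 mg and state the exit. On resolution within 4 weeks the patient steps to 300 mg, as an explicit exception to the one-month wait; the wait then applies before 400 mg. Toxicity still present at 4 weeks leads to discontinuation, as now.

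With this wording a patient at 200 mg reaches 300 mg on day d and 400 mg no earlier than day d + 28.

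**Cost.** A protocol amendment, with authority and ethics approval if classed as substantial (17.10). Affected patients spend at least 4 weeks at 300 mg before returning to 400 mg.

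**Optional.** Applying the wait to Grade 2 reductions, or allowing about 8 weeks at 200 mg (28 + 28 = 56 days) to fit a toxicity-free month there, are trade-offs for the sponsor and are not needed to remove the conflict. The undefined suboptimal-response sentence in 11.6.1.2 is a separate minor clean-up.

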11.6.1.1 Management of Non-Hematologic Treatment-Related Toxicities

The management of non-hematologic treatment-related toxicities is summarized in Table 1.

Table 1. Non-Hematologic Treatment-Related Toxicities

Adverse Event	Action
Elevated liver transaminases	If elevations in liver transaminases (ALT, AST) $> 5 \times$ institutional upper limit of normal (ULN) occur, bosutinib should be interrupted until recovery to $\leq 2.5 \times$ ULN and may be resumed at 400 mg once daily thereafter. If recovery takes longer than 4 weeks, discontinuation of bosutinib should be considered. If transaminase elevations $\geq 3 \times$ ULN occur concurrently with bilirubin elevations $> 2 \times$ ULN and alkaline phosphatase $< 2 \times$ ULN, bosutinib should be discontinued.
Diarrhea	For Grade 3/4 diarrhea, bosutinib should be interrupted and may be resumed at 400 mg once daily upon recovery to Grade ≤ 1 .
Grade 1	Current dose level

Grade 2	For persistent clinically relevant toxicity ^b not responding to optimal management: Temporarily interrupt treatment, and reintroduce at the same dose or reduce dose by 1 level upon recovery to Grade ≤ 1 within 4 weeks of stopping test article.
Grade 3 ^a	For persistent clinically relevant toxicity ^b not responding to optimal management: Withhold treatment, then dose reduce by 1 level upon recovery to Grade ≤ 1 within 4 weeks of stopping test article. If recovery takes longer than 4 weeks, the Investigator should contact the Sponsor to determine if the patient may continue on treatment.
Grade 4 ^a	Withhold treatment. Investigator and Sponsor to review to determine if patient may continue on treatment with appropriate dose reduction.
	
a. For patients requiring dose reduction due to toxicity, who have been free of the toxicity (Grade ≤ 1) for at least 1 month and are otherwise tolerating study drug, the Investigator may choose to re-escalate dose by 1 dose level back to starting dose.b. Persistent Clinically Relevant Toxicity is defined as - symptoms of toxicity which, despite optimal medical management, persist for ≥ 14 days ("persistent") and cause sufficient symptoms or signs of illness in the subject to warrant further intervention, i.e. dose adjustment ("clinically relevant").

Subjects with Grade 3 non-hematological toxicity that does not respond to optimal management, will be managed by withholding treatment, followed by dose reduction by 1 level upon recovery to Grade ≤ 1 . If, on re-challenge at reduced dose, the subject remains free of toxicity (Grade ≤ 1) for at least 1 month, the Investigator may choose to re-escalate the dose by 1 level back to the starting dose.

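### Table 1 allows bosutinib to restart at a fixed 400 mg after Grade 3/4 diarrhea, which conflicts with the rules for Grade 4 and unresponsive Grade 3 events and ignores the dose at onset

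*Protocol*

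**What the plan says.** All rules below are in the protocol. The SAP has none on bosutinib dose modification. Section 11.1 sets the study dose at 400 mg/day.

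- **Table 1, diarrhea row:** "For Grade 3/4 diarrhea, bosutinib should be interrupted and may be resumed at 400 mg once daily", once recovered to Grade 1 or better.
- **Table 1, transaminase row:** after interruption and recovery, bosutinib "may be resumed at 400 mg once daily thereafter".
- **Table 1, Grade 4 row:** withhold, then "Investigator and Sponsor to review to determine if patient may continue on treatment with appropriate dose reduction".
- **Table 1, Grade 3 row:** "Withhold treatment, then dose reduce by 1 level upon recovery". This applies to persistent, clinically relevant toxicity that optimal management has not controlled. Footnote b defines persistent as 14 days or more.
- **Table 1, footnote a:** after a reduction and at least one month free of the toxicity, "the Investigator may choose to re-escalate dose by 1 dose level back to starting dose".
- **Section 11.6.1.1, paragraph after Table 1:** when optimal management fails for a non-hematological toxicity of Grade 3, the patient "will be managed by withholding treatment, followed by dose reduction by 1 level upon recovery". If the patient then stays free of toxicity "for at least 1 month, the Investigator may choose to re-escalate the dose by 1 level back to the starting dose". Diarrhea is not excepted, and the 14-day condition does not appear.
- **Section 11.6.1:** reduction to 300 mg is permitted for toxicity possibly related to bosutinib. Reduction to 200 mg needs Sponsor approval and an optimum response, and lasts at most 4 weeks. A reduced patient stays at that dose unless the toxicity resolves. On resolution: "In that case, the dose can be escalated to the previous starting dose". Re-escalation from 200 mg is referred to the escalation guidelines.

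**The concern.** The diarrhea row covers Grades 3 and 4 together and names one restart dose, the full one. It asks for no Sponsor review, sets no condition on persistence or response, and does not mention the dose the patient was taking. Other rules in the same section prescribe review or reduction for some of the same events.

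Two sites could therefore both follow the protocol and give different doses after the same severe event. A patient who had already needed a reduction could be put back on 400 mg directly after a new severe toxicity. Diarrhea is the toxicity most likely to bring this up: section 6.2 calls it the most frequent side effect of bosutinib, and section 13.9.1 lists Grade 3-4 diarrhea as an event of special interest.

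**Working it through.** The plan states no figure to reproduce here. The check compares the rules and then does simple dose arithmetic.

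**Step 1. Which events conflict.**

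| Diarrhea event, onset at 400 mg | Diarrhea row allows | Other rule | Conflict |
|---|---|---|---|
| Grade 3, responds to management | 400 mg | none requires a reduction | no |
| Grade 3, unresponsive, under 14 days | 400 mg | paragraph after Table 1: 300 mg | yes |
| Grade 3, unresponsive, 14 days or more | 400 mg | that paragraph and the Grade 3 row: 300 mg | yes |
| Grade 4 | 400 mg, no review | Grade 4 row: review, then a reduced dose | yes |

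**Step 2. Is precedence stated?** No. Section 11.6 sends exceptions to the Medical Monitor but does not say which row is the rule and which would be the exception.

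**Step 3. Dose at onset.** The dose levels are 400, 300 and 200 mg (section 11.6.1).

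- Onset at 300 mg: 400/300 = 1.33, a 33% increase (one level).
- Onset at 200 mg: 400/200 = 2.00, a 100% increase (two levels). Footnote a speaks of one level.

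For persistent, unresponsive Grade 3 diarrhea starting at 300 mg, the diarrhea row allows 400 mg, while the Grade 3 row leads to 200 mg with Sponsor approval. If the earlier toxicity has not resolved, a restart at 400 mg is also at odds with section 11.6.1. If it has resolved but not yet been clear for a month, the restart is at odds with footnote a. If it has been clear for a month, a step from 300 to 400 mg does not breach footnote a as far as that earlier toxicity is concerned.

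**Step 4. Waiting time.** Section 11.6.1 states none before return to the starting dose. Footnote a and the paragraph after Table 1 require at least one month. The 4-week limit at 200 mg adds a difficulty. Taking a month as one 28-day cycle (the convention in section 12.1), a toxicity that resolves on day d of a 200 mg spell would be clear for a month only at d + 28, which is past the 28-day limit for any d above 0.

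**Step 5. How many patients.** Section 6.2 gives under 10% Grade 3-4 diarrhea on bosutinib. Expected count: below 36 × 0.10 = 3.6 of 36 patients. The documents do not split this into Grade 4, unresponsive Grade 3 and the rest, so the conflicting subset cannot be computed.

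**The case against.** The strongest defence is that a named toxicity overrides a generic grade. The named rows come first in Table 1, and the transaminase row carries its own 4-week and bilirubin rules, as a self-contained row would. That reading is possible, and the Grade 4 conflict does rest on the table layout. But the protocol does not state it, and the Grade 3 rule also stands in running text without an exception for diarrhea. Even if the named row governs, its fixed dose still ignores the dose at onset.

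Other points stand and limit the concern:

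- *May* is permissive, and section 11.6.1 separately allows 300 mg for toxicity possibly related to bosutinib. A reader might infer that the protocol requires 400 mg, or rules out reduction for diarrhea. It does neither.
- A reader might infer that the plan endorses doubling the dose from 200 mg. That follows only from the diarrhea row read alone, since section 11.6.1 sends re-escalation from 200 mg through the escalation guidelines. The 200 mg level is also restricted and brief.
- During combination therapy, Table 5 requires Sponsor contact for Grade 4 diarrhea, and for Grade 3 if it does not resolve. Related Grade 3 or 4 non-hematological events also count as dose-limiting toxicities (section 9.3.1). These bring oversight but do not set the bosutinib dose. In 1 + 12 = 13 of the 25 cycles bosutinib is given alone.

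**Conclusion.** The concern holds within limits. For Grade 4 diarrhea, and for Grade 3 diarrhea that does not respond to optimal management, Table 1 permits a full-dose restart where other rules call for review or reduction, and no precedence is given. Separately, the fixed 400 mg in the diarrhea and transaminase rows takes no account of an earlier reduction, and section 11.6.1 omits the one-month wait required elsewhere.

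The conflict should not be extended to all Grade 3 diarrhea: an event that starts at 400 mg and responds to management raises none. Nor is 3.6 of 36 a ceiling. It is an expected count that assumes the bosutinib figure in section 6.2 carries over. Section 6.3 lists diarrhea as common with atezolizumab too, so the combination rate could be higher.

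This is a dosing-safety point for few patients and should be fixed. No sample size, estimate or analysis changes.

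**What to change.** 1. In the diarrhea and transaminase rows of Table 1, replace the fixed 400 mg restart with *a dose not exceeding the dose at event onset*.
2. State that Grade 4 events, and Grade 3 events that do not respond to optimal management, follow the grade rows for these named toxicities too.
3. Make the re-escalation sentence in section 11.6.1 refer to the one-month condition in footnote a. The sponsor should reconcile that condition with the 4-week limit at 200 mg; how to do so is a clinical decision.

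The cost is a text amendment to section 11.6.1 and Table 1. It needs no extra visits, tests or patients.
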